### **1. PURPOSE OF THE STUDY AND BACKGROUND**

The clinical, economic and scientific challenges associated with AF triggered the National Heart, Lung and Blood Institute to convene a panel of experts to recommend research directions and strategies for AF prevention. The panel defined recommendations in six well-defined fields of research including “the improvement of AF detection by using emerging methods and technologies”.

#### **1.1 Purpose of the study**

We propose to evaluate the robustness of a novel technology used at home for AF detection that is innovative because it is less intrusive than current monitoring options (contactless) and inexpensive. We believe this novel monitoring strategy could address the current challenge of modern medicine around the detection of sub-clinical AF.

#### **1.2 Background**

We propose to shift the paradigm of clinical management of AF patients by using a unique and novel monitoring technology that will be easily and readily available to patients (by downloading an application on a smart device embedding a web camera, without the need for additional sensors), and therefore will enable ubiquitous and contactless testing of individuals with risk to develop AF. We believe the proposed technology could be used for the detection of sub-clinical AF. Approximately 15% of ischemic strokes are directly attributed to emboli in the setting of AF. And, nearly 25% of additional ischemic strokes in which no cause can be identified may also be due to asymptomatic AF. Healey et al described the incidence of sub-clinical AF in a large cohort of patients who had undergone recent implantation of a pacemaker or defibrillator; these patients were at high risk for stroke and did not have a known history of AF. By 3-month follow-up, 10.1% of patients had an AF event documented by the device, and AF occurrence was associated with a significant increased risk of ischemic stroke or systemic embolism. Therefore, a substantial percentage of patients with AF have no symptom even during sustained episodes of AF. These characteristics of AF make its detection a real challenge that is not addressed by the current monitoring solutions.

This ineffectiveness of current monitoring strategies for the detection of sub-clinical AF has also been highlighted in the CRYSTAL AF clinical trial. In this study, the patients with a history of cryptogenic stroke but with no clinical history of AF were randomized to conventional follow-up versus implantable cardiac monitor. AF was detected in 8.9% and 1.4% of patients with implantable cardiac monitor and conventional follow-up, respectively. This study demonstrates the importance of developing methods that allow for more ubiquitous monitoring. Recent data have suggested that even short episodes of sub-clinical AF can have devastating clinical consequences. Patients with newly implanted pacemakers with detected AF episodes  $\geq$  5 minutes had a significant increase in cardiovascular mortality and stroke mortality. This data again emphasizes the importance of detecting all sub-clinical episodes of AF even if the episodes are of very short duration.

#### **1.3 Objectives**

**Our primary aim** is to assess the performance of the Videopethysmographic (VPG) technique of the face and finger to detect AF using a tablet operated by the patient at home. Simultaneous ECG recordings using a continuous recorder that is an ECG patch device will validate the presence of AF at the time of the video recording.

**Our secondary aim** is to investigate the benefit of acquiring a VPG recording just after successful AF cardioversion/ablation in sinus rhythm. We will evaluate if the VPG-based signal measured during sinus rhythm can be used to improve (in comparison to the results of AIM 1) the detection of early-recurrence of AF events.

**Our tertiary aim** is to estimate the distribution of the time from first onset of AF (as detected via ECG) until the first true AF detection by VPG. Of particular interest is the probability of detecting AF within 48 hours after the onset of the arrhythmia, which can be viewed as a 48-hour sensitivity of the VPG monitoring process. Similarly,

we will estimate the distribution of the time from hospital discharge (in sinus rhythm) until the first false AF detection by VPG. Each point on the latter curve can be interpreted as the specificity of the VPG monitoring process as a function of follow-up time.

#### **1.4 Study Device/Supplies Administration**

The Project Manager will be responsible for receipt, storage, dispensing, collection, accountability and disposal of all program devices and supplies. All devices and supplies will be identified by their specific Model, Serial, and/or Part Numbers; and will be tracked using an equipment/supplies inventory computer program resident in the ECG Core Laboratory (ECL) of the Heart Research Follow-up Program. All equipment and supplies will be logged in the system, and monitored by the Project Manager. The ECL IT manager will be responsible for maintaining all equipment required for the conduct of the study. All devices and supplies will be stored in the ECL secure storage room.

### **2. STUDY DESIGN**

#### **2.1 Overview**

In this proposal, we plan to evaluate the technology when used by patients at home. One of the major challenges in designing the proposed study is to ensure that one can capture ECG and video recordings during AF in ambulatory patients while minimizing the size of the patient cohort and the duration of the follow-up period.

#### **2.2 Rational for study design**

We will provide a Samsung Tablet (Tab III) or an iPad to the enrolled subjects before they are released from the hospital. Mobile smart devices are used ~3 hours per day on average, and we will use this time spent on the device to capture VPG signals. Indeed, our technology, when installed on a tablet, can run in the background. The application will automatically be triggered when the subject switches on the device, and while the subject interacts with the device during internet browsing or watching videos. This recording concept will provide previously unattainable streams of data, with no limit in recording duration and number of recording sessions, to analyze pulse variability and identify the presence of AF.

### **3. CHARACTERISTICS OF THE RESEARCH POPULATION**

#### **3.1 Subject Characteristics**

We opted to enroll two sets of symptomatic patients with paroxysmal or persistent AF 1) scheduled for ablation treatment ), and 2) treated by electrical cardioversion. We selected these cohorts of patients because ~40% of patients with successful AF ablation and ~30% in patients successfully converted by electrical shocks are expected to experience early recurrence of symptomatic AF (ERAF) during the following 14 days. As a note, increasing the follow-up period to 60 days would increase the number of ERAF by only 10%. Oral et al. studied the symptomatic ERAF in 110 patients after ablation treatment (pulmonary vein isolation) for either paroxysmal or persistent AF. Their observational study reported that 35% of the patients had a recurrence of symptomatic ERAF at a mean 3.7+-3.5 days after the procedure. Figure 4 provides the distribution of the ERAF for a 60-day follow up period. In an independent study, Lee et al. reported 39% of symptomatic ERAF in a cohort of 207 patients who received ablation (focal or isolation procedure) for paroxysmal AF. Recently, Chang et al. characterized symptomatic ERAF in the same type of patient cohort i.e. 339 patients with symptomatic drug-refractory AF treated by ablation. Their work described a 34% of early recurrence of AF in patients with non-paroxysmal AF, and 15% in patients with paroxysmal AF. As reported by Andrade et al. (see Table I in ) on the incidence of symptomatic ERAF after ablation, it is not uncommon that patients treated by catheter ablation experience symptomatic ERAF with an incidence between 30% and 50%. For the rate of ERAF in patients with electrical transthoracic cardioversion, the literature is rather poor. Bainconi et al., Yu et al., and Siaplaouras et al. reported ERAF reaching 26%.

##### **3.1.1 Number of subjects:**

The project is designed to gather two sets of data during a period of 35 months: learning and validation. We will acquire the data from the learning group during the first 17 and a half months of the study. During an additional period of the same length, we will enroll the patients for the validation dataset (50% split). We have planned to enroll 315 patients on a 3-year period for the learning and validation groups.

We believe we will not be able to enroll all AF patients coming to the URMC clinic. Based on previous studies (preliminary results) conducted at URMC, we expect an enrollment rate of ~60%.

- The number of symptomatic AF patients (persistent or paroxysmal) treated by electrical cardioversion at the University of Rochester Medical Center has been in the order of 120 patients per year. We will enroll ~210 subjects (from a pool of 350 patients) during the study period of 35 months.
- There are ~60 symptomatic patients treated by ablation techniques every year at URMC. We intent to enroll~105 of these subjects (from a pool of 175 patients) during the study period of 35 months.
- Because of the relative shortness of the actual study period (2 weeks), we project a potential subject withdrawal rate (by the subject or via subject non-compliance to protocol) at less than 1%. Therefore, subject withdrawal should not require an increase in the projected subject enrollment numbers. Hence, we will enroll 315 patients and expect to get ~284 patients successfully converted (90% of the cohort, see Table 1).

|                   | AF Patients | Study Pool | Enrolled (60%) | Converted (90%) | ERAF     | NO ERAF |
|-------------------|-------------|------------|----------------|-----------------|----------|---------|
|                   | 12 months   | 35 months  |                |                 |          |         |
| Ablation Pts      | 60          | 175        | 105            | 95              | 38 (40%) | 57      |
| Cardioversion Pts | 120         | 350        | 210            | 189             | 57 (30%) | 132     |
|                   | Total       | 315        | 284            | 95              | 189      |         |

**Table 1: Table describing the estimated number of patients treated by ablation or electrical cardioversion who are available at the URMC clinic per year (column 1), during the overall time of the study enrollment period (column 2), enrolled in the study (column 3), successfully converted (column 4) and ultimately experiencing ERAF (column 5).**

### 3.1.2 Gender and Age of subjects:

We will enroll adult patients only. AF is a disease that is usually not observed in children and teenagers. The prevalence rates of atrial fibrillation are higher in men compared with women in both the United States and globally. In the largest cotemporary cohort of almost 18,000 patients in the United States, AF prevalence was approximately 30% higher in men as compared to women. These prevalence differences were even more pronounced when looking at global burden of atrial fibrillation. In 2010, global prevalence rates (per 100,000 population) were 569.5 in men and 359.9 in women. The prevalence rates of atrial fibrillation are higher in men than in women in every age group and study enrollment would be expected to reflect these gender specific differences.

### 3.1.3 Racial and Ethnic origin:

The distribution of races and ethnics will be representative of the pool of patients with AF in Rochester community. We present in Table 2, the estimated distribution for the cohort of 315 subjects

| TARGETED/PLANNED ENROLLMENT: Number of Subjects |            |       |       |
|---|------------|-------|-------|
| Ethnic Category                                 | Sex/Gender |       |       |
|   | Females    | Males | Total |
| Hispanic or Latino                              | 10         | 10    | 20    |

|   |    |     |     |
|---|----|-----|-----|
| Not Hispanic or Latino                            | 89 | 206 | 295 |
| Ethnic Category: Total of All Subjects *   | 99 | 216 | 315 |
| Racial Categories                          |    |     |     |
| American Indian/Alaska Native                     | 0  | 0   | 0   |
| Asian   | 3  | 4   | 7   |
| Native Hawaiian or Other Pacific Islander         | 0  | 0   | 0   |
| Black or African American                         | 19 | 19  | 38  |
| White   | 73 | 197 | 270 |
| Racial Categories: Total of All Subjects * | 95 | 220 | 315 |

Table 2: Distribution of races and ethnics in the proposed cohort of AF patient enrolled in our project.

### 3.2 Inclusion and exclusion criteria

#### 3.2.1 Inclusion criteria:

- Men and women older than 18 years of age,
- Medically-managed for symptomatic AF (persistent or paroxysmal),
- In sinus rhythm after their ablation procedure,
- In sinus rhythm after trans-thoracic electrical cardioversion.

#### 3.2.2 Study Exclusion criteria:

- Implanted with a device (pacemaker, CRT, ICD) and a ventricular pacing requirement superior or equal to 70%,
- Known allergic reaction to adhesives or hydrogels or with a family history of adhesive skin allergies,
- Unable to cooperate with the protocol due to dementia, psychological, or other related reason,
- Refusing to sign the consent for participation,
- Unable to operate the device such as blind patients.
- Patients with Parkinson disease (or other central nervous system disorder/Tremor) who cannot record a stable video signal of their face.
- The subject was previously enrolled in the current study.
- The subject wears clothing covering the face, or uses facial makeup that will interfere with the quality of facial recordings.
- Subject does not have internet access at home and lacks the technology to participate.

#### 3.2.3 Discussion of subject population:

The electrical cardioversion is a procedure that is not used in pregnant women; therefore we do not expect to enroll pregnant women in the AF arm of the study, i.e., patients prescribed with electrical cardioversion.

#### 3.2.4 Vulnerable subjects

For University of Rochester employees who may be approached to participate as subjects in this project: Taking part in this research will not be considered as a part of their University duties, and refusing to participate will not affect their job(s). They will not be offered or receive any special job-related consideration if they take part in this research.

## **4. SUBJECT IDENTIFICATION , RECRUITMENT AND CONSENT**

### **4.1 Methods of Subject Identification and Recruitment**

The study population will be drawn from the pool of AF patients prescribed with ablation and cardioversion at the University of Rochester Medical Center (Rochester, NY). The patients will be identified by a research staff member who will review the list of patients scheduled for either electrical cardioversion or AF ablation at the URMC (cardiology). Cardiac patients identified during a scheduled clinic visit will be given the option of taking the consent form home to review. Prior to returning to the University of Rochester Medical Center for their procedure (ablation/cardioversion), patients may be contacted by phone (by a research staff member, using the study's approved Oral Script) to assess their interest in participating in the project (given their understanding that they subsequently meet project inclusion criteria after their procedure), as well as specific questions regarding previous computer experience and internet access at home.

### **4.2 Process of consent**

The consent forms will be subsequently signed by the patient, if the patient is still willing to be involved and meet the inclusion criteria of the study as described above. The project consent forms will be stored in specific folders in the secure clinic confidential material file room, and managed by a research staff member. On a weekly basis, the stack of consent forms will be delivered to the HRFUP ECG Core laboratory for storage in the HRFUP secured filing room. A copy of the signed consent forms will be provided to the enrolled patients. Co-investigator, [name] (Cardiology, URMC) will not consent subjects

## **5. METHODS AND STUDY PROCEDURE**

We will provide a Samsung Tablet (Tab III) or an iPad Pro to the enrolled subjects before they are released from the hospital. Mobile technology is used ~3 hours per day on average, and we will use this time spent on the device to capture VPG signals. Indeed, our software application, when installed on a tablet, can run in the background. The application will automatically be triggered when the subject switches on the device and during various allowable activities performed with the device. The use of the tablet will be limited to watching videos, and accessing YouTube as well as a variety of other public websites. The type of applications (APPs) available to the subject will slightly differ between devices (iPad and Samsung TAB). This recording concept will provide previously unattainable streams of data, with no limit in recording duration and number of recording sessions, to analyze pulse variability and identify the presence of atrial fibrillation. To protect subject's privacy, the access to the email software will be password protected using a password known only by the subject. Furthermore, the subject will be trained to know how to delete the browsing history and cookies from the tablet browser before he/she return the device with the video recordings. Password protection for accessing the Tablet itself would be problematic since it would have to change with every new subject using the device. In addition, the sophistication of the facial recognition software utilized in the study allows the filtering out of images of individuals other than the subject, and, therefore, effectively nullifies the need for the password protection.

The enrolled subjects will be asked to record facial and finger videos for at least 30 seconds : 1) twice a day during a period of 14 days following their procedure, 2) when they feel AF symptoms (~33% should experience symptomatic ERAF), and 3) prior to hospital discharge for the purpose of establishing a baseline recording during sinus rhythm (30 second period). Importantly, before the subjects' hospital release, they will be trained by a research staff member regarding EKG Patch attachment and maintenance; how to operate the tablet VPG, Symptoms, and general applications; and how to obtain technical support during the study period . The subject will subsequently participate in a Pre-Study survey regarding the quality of the training, retention aspects of the training, and their understanding of study support that will be available for them. The subject will be asked the questions in Part A and Part B of the survey by study staff prior to the subjects return to home. The subject will be called by a member of our team within 24-48 hours following their return home from the hospital to ask the remaining Pre-Study survey questions (Part C.), and to verify that the Tablet could be connected to their home WIFI system. If they were unable to connect the tablet, technical support (by the

Project IT manager) will be provided via telephone to assist the subjects in establishing the connection. Subjects may also be contacted by a project team member at 7 and 11 days into their study period to support subject compliance, and to answer any questions the subject may have regarding the study technology. On the last day of their study period (day 14) the subjects will again be contacted by a member of our team to go over any questions the subject may have regarding their EKG Patch removal and the shipping of the patch and the tablet back to the Study Center (the ECG Core Laboratory at the Heart Research Follow-up Program). On or about day 14, subjects will be asked to participate in a Post-Study survey that assesses their general satisfaction and experiences with the study, its staff, and the technology utilized in the study. The survey will be administered to the subject by study staff over the phone. Within 2-weeks of completion of their study period, subjects will be sent a "Thank You" letter from the PI, thanking them for their participation in the study.

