- *Zio XT® ECG patch:* the usability of the patch and the quality of the ECG recording are of no concern in our study because this device is already a fully validated clinical device. From a logistic point of view, the subject will start wearing the patch before s/he leaves the hospital. The patch is placed on the flattest part of the upper left chest, its location is defined using 1 finger width below the collarbone, centered over the left pectoral muscle with the edge of the ZIO Patch next to the sternum, and with an angle so that the arrow on the top patch label points upward. It is important to avoid armpit and breast tissue. There is no activity restriction when the subject wears the ECG patch. The subject will receive a package to mail both the tablet and the patch at the end of the monitoring period (14 days) to the ECG Core Laboratory (ECL) of the Heart Research Follow-up Program. The ECL will 1) load the VPG data from the tablet for processing and 2) will mail the patch to iRhythm for analysis and ECG signal extraction. This data will be available electronically to the ECL using a secured BOX™ server (cloud technology already used by the HRFUP in several FDA-regulated clinical trials).
- *The iPad and Samsung TAB III tablet:* the tablet will provide the following functionalities: 1) VPG monitoring during the time the tablet is used, and 2) a symptom reporting APP that needs to be triggered by the subject if he/she feels AF symptoms, and 3) a Notification APP that will be automatically triggered to insure subject compliance to the protocol.
  - VPG monitoring:

The tablet will automatically acquire the facial video of the subject when it is in use. Subjects will be asked to utilize the tablet a minimum of 5 minutes, twice a day (in addition to scheduled and symptomatic recordings). The tablet will record successive 30 sec. facial video recordings, extract the information from the video, and send the data to a secured cloud-server (BOX.com). A single picture of the face of the subject will be extracted from the video (at the beginning of each 30sec. recording). This image will be encrypted and sent with the

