## **8.2 Implementation of the Learning and Validation steps**

It is important to note that during the Validation phase of the project, [name] PhD, MBA will be excluded from evaluating the performance of the VPG technology because of the potential for a conflict of interest. His role during this phase of the project will be that of a technical consultant only. In addition, for the validation phase, blinded study data will be sent to RIT for processing and the results will be sent to [name] (U of R) for evaluating the performance of the tested technology to detect the presence of AF. [name], Department of Biostatistics, will be responsible for the statistical analysis of the clinical data at the UR.

**-AIM1, Detection Performance of VPG:** To address Aim 1 we will use the Training Data) to construct a classifier to predict AF as a function of facial VPG measures, then we will use the Validation Data to provide an unbiased characterization of its performance on independent subjects. Each subject will record a baseline VPG during sinus rhythm. During the 2-week follow-up period, subjects will be asked to record a video selfie (VPG) twice per day, each synchronized with the ECG recording from the Zio patch. Subjects will be asked to perform additional VPG recordings any time they feel symptomatic. The longitudinal binary outcome at each follow-up time will be AF as determined by ECG. We expect to have a minimum of 29 outcomes per patient (2 weeks x 7 days/week x 2 recordings/day + 1 baseline) x 142 patients (half of the 315 enrolled x 90% converted) = 4K outcomes in the Training Data (and similarly in the Validation Data), each with an associated VPG from which the 8 VPG measures described above (PR, heart rate, RMSSD, SDRR, pNN50, SD1, SD2, AFEvidence) will be calculated.

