We will also construct ROC curves based on the Validation Data to display the trade-off between sensitivity and specificity as a function of the threshold for the linear predictor, and we will compare these to cross-validation-based (as well as optimistic naïve) ROC curves based on the Training Data. To investigate calibration, we will fit a marginal logistic model to the Validation Data with the un-thresholded linear predictor as the sole predictor. Testing the null hypothesis that the slope in this model is 0 tests whether the model is useless, and thus we hope and expect to strongly reject this null hypothesis with a tiny p-value; testing the null hypothesis that the slope is 1 is a test of calibration, and we hope that we fail to reject this null hypothesis with a large p-value (indicating good calibration). We will also use the Validation Data to re-estimate all of the individual coefficients in the marginal logistic regression model, for comparison with the potentially biased estimates from the Training Data.

**-AIM2: Benefit of using Baseline VPG Recording:** Each subject will have a baseline VPG recorded during sinus rhythm (using the Samsung Tablet). This recording will be acquired after successful procedure and before the subject leaves the hospital. Sinus rhythm will be checked by health professional. To address Aim 2, we will repeat the above general procedure but based on the *differences* from baseline in VPG measures and/or by including the baseline VPG measures along with the instantaneous VPG measures for predicting AF at each time point. When the time comes to open the Validation Data, we will compare the sensitivity and specificity of the classifier from Aim 2 to that of Aim 1 to quantify the potential improvement due to incorporating a baseline VPG.

[figure not shown]

Figure 7: Schematic presentation illustrating the true and false detection of AF and SR rhythm during the 14-day follow-up period of the study. The upper line represents the continuous ECG recording (either blue or black for SR and AF, respectively), while the lower line presents the same 14-day period during which VPG will be recorded. The VPG monitoring periods in which 5 recording sessions are marked (limited to 5 for clarity purpose). We will have at least 2 recording sessions per day, i.e., 28 recordings sessions.

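### Aim 2 takes its baseline from one 30-second clip per patient, with no repeatability figure and no repeat or averaging rule, so the estimated gain from a baseline is attenuated by an unknown amount

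*Combined protocol and SAP*

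**What the plan says.** Section 1.3 states the secondary aim: "We will evaluate if the VPG-based signal measured during sinus rhythm can be used to improve" detection of early recurrence relative to Aim 1. Section 5 asks patients to "record facial and finger videos for at least 30 seconds" on each occasion, but gives the baseline its own length: "prior to hospital discharge for the purpose of establishing a baseline recording during sinus rhythm (30 second period". The outcome count in Section 8.2 has one such recording per patient ("2 recordings/day + 1 baseline").

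For Aim 2, Section 8.2 repeats the Aim 1 model building with differences "from baseline in VPG measures and/or by including the baseline VPG measures along with the instantaneous VPG measures". The plan does not commit to either form. The final step, at the validation stage, reads: "we will compare the sensitivity and specificity of the classifier from Aim 2 to that of Aim 1 to quantify the potential improvement".

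Section 5.1 describes a video quality screen and daily checks of the data sent from home. The documents give no repeatability for the 30-second measures, no rule for averaging or repeating the baseline, and no power, margin or interval method for the Aim 2 comparison.

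**The concern.** The baseline is measured once and used in every later comparison for that patient. Follow-up recordings carry fresh error each time, but the baseline's error is the same in all 28, so more follow-up does not average it out. Several of the eight VPG measures (RMSSD, SDRR, pNN50, SD1, SD2) are beat-to-beat variability statistics, which are imprecise over a few dozen beats.

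At stake is the reading of Aim 2. As planned, a small gain could mean that a patient's own sinus-rhythm signal adds little, or that it was measured too imprecisely to show what it adds. The baseline is by definition taken before discharge, so an unusable clip cannot be replaced later.

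**Working it through.** **The plan's own figures.** Recordings per patient: 2 weeks x 7 days x 2 + 1 = 29, and 29 x 142 = 4,118, the stated 4K. The only power figure, 75-96% for Aim 1, also reproduces: with the one-sided 0.05 exact binomial test of 70% against 85%, power over n = 50 to 92 runs from 75.4% (n = 52) to 96.1% (n = 89). Nothing comparable is given for Aim 2, so what follows is an illustration.

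**Assumptions.** One normally distributed measure with total variance 1; between-patient share ICC, within-patient share 1 - ICC; the same patient effect in sinus rhythm and AF; Aim 1 sensitivity = specificity = 85%, the value Section 8.2 hopes for. Then accuracy (sensitivity = specificity) = Φ(1.036/√V), where V is the error variance of the score and Φ(1.036) = 0.85. Let k be the number of baseline clips and s the share of baseline error common to all clips of the session.

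**Difference form.** V = (1 - ICC)(1 + s + (1 - s)/k).
- One clip: V = 2(1 - ICC). This is below 1, the Aim 1 value, only if ICC > 0.5.
- Five clips: the bracket is 1.20, 1.60 or 1.84 for s = 0, 0.5 or 0.8. The break-even ICC is 1 - 1/bracket = 0.17, 0.375 or 0.46.

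**Covariate form.** V = 1 - ICC²/(ICC + (1 - ICC)(s + (1 - s)/k)). This never exceeds 1, so a noisy baseline shrinks the gain but does not reverse it.

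| ICC | Form | 1 clip | 5 clips, s = 0.8 | 5 clips, s = 0.5 | 5 clips, s = 0 |
|---|---|---|---|---|---|
| 0.3 | Difference | V 1.40: 80.9% | V 1.288: 81.9% | V 1.12: 83.6% | V 0.84: 87.1% |
| 0.3 | Covariate | V 0.910: 86.1% | V 0.899: 86.3% | V 0.875: 86.6% | V 0.795: 87.7% |
| 0.5 | Difference | V 1.00: 85.0% | V 0.92: 86.0% | V 0.80: 87.7% | V 0.60: 91.0% |
| 0.5 | Covariate | V 0.750: 88.4% | V 0.728: 88.8% | V 0.688: 89.4% | V 0.583: 91.3% |

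At s = 1 five clips give the same result as one.

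**Why 30 seconds is short.** At an assumed 60-100 beats per minute a clip holds 30-50 beats. If beats are independent, the relative standard error of an SD-type measure is 1/√(2(n - 1)): 13.1% for n = 30 and 10.1% for n = 50. Averaging five clips divides this by √5, to 5.9% and 4.5%. This component averages out; session-level error does not.

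**The case against.** A reader might infer that the trial could conclude a baseline has no value solely because the clip was too short. The documents do not support that, for four reasons.

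- Section 8.2 allows the baseline measures as separate predictors. In the model above one clip then still helps, even at ICC 0.3 (86.1% against 85.0%). Predictors are selected on the Training Data, so a harmful difference form can be dropped before the Validation Data are opened.
- The plan has no rule for declaring no benefit; it quantifies an improvement.
- A null result has other possible causes, notably few AF patients. For a paired comparison of 85% with 90%, one-sided 0.05, one observation per patient and an assumed discordance p of 5-15%, power is Φ((0.05√n - 1.645√p)/√(p - 0.05²)): about 23-47% for n = 50 and 34-70% for n = 92.
- The missing ICC could be estimated from data already planned: 28 scheduled follow-up recordings per patient with ECG-determined rhythm, and 189 of 284 converted patients expected to have no early recurrence. The plan does not say that this will be done.

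Two further points stand. Back-to-back clips share posture, lighting and post-procedure state, so five may add little (86.0% at 80% shared error). Section 1.3 also asks about a single recording after the procedure, so averaging five changes the tested procedure somewhat. A reader might also infer that a clip failing the quality screen leaves the patient without a baseline; the documents neither say that it is discarded nor provide for a repeat.

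None of this removes the core: one clip, error shared across all comparisons, and nothing in the plan to measure or reduce that error.

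**Conclusion.** The concern holds as a limit on precision and interpretation. Aim 2's only added information is one 30-second clip of unstated repeatability, so the estimated benefit of a baseline is attenuated in either form: a difference score needs ICC above 0.5 to gain at all, and a covariate gains less than it could. At ICC 0.5, five clips instead of one are worth 1.0 to 6.0 points in the difference form and 0.4 to 2.9 points in the covariate form, for shared error from 80% down to none. At ICC 0.3 the covariate gain is only 0.2 to 1.6 points.

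These sizes rest on an ICC and a shared-error fraction that the documents do not give, on one normal measure standing in for an eight-measure classifier, and on a patient effect that carries over from sinus rhythm to AF. They show direction and plausible range and do not forecast the trial's result. The change is a cheap improvement, not the repair of a fatal flaw.

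**What to change.** - **Section 5, baseline item:** record about five successive 30-second facial clips in confirmed sinus rhythm before discharge, with a repeat before the patient leaves if none passes the quality screen. Section 5.1 already says "The tablet will record successive 30 sec. facial video recordings", and the tablet is issued before discharge. Aim 1 is built on facial measures, so extra finger clips are needed only if a finger-based classifier is analysed.
- **Section 8.2, Aim 2:** define each baseline measure as the mean or median over the clips that pass. The first clip can still be analysed alone, so the single-recording question in Section 1.3 is kept.
- **Section 8.2, reporting:** report the repeatability of each sinus-rhythm measure from the ECG-confirmed follow-up recordings, so that a small Aim 2 gain can be interpreted.

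Cost: four extra clips x 30 seconds = 2 minutes of recording plus handling, so a few minutes per patient, with no new equipment, and a few lines of text. The clips reduce within-session error only; between-day and hospital-to-home variation remain. The pre-discharge part must be in place before patients are enrolled, because the recording cannot be made afterwards.
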